Secondary Outcome:	change in absolute cardiovascular risk
Timepoint:	at 12 and 24 months post baseline, and 12 months post intervention
Secondary Outcome:	proportion of participants achieving individualised HbA1c targets according to the Australian Diabetes Society guidelines
Timepoint:	at 12 and 24 months post baseline; also 12 months post intervention
Secondary Outcome:	impact on psychometric scores as assessed using the Assessment of Quality of Life (SF-36), Patient Health Questionnaire (PHQ-9) [Depression] and Generalised Anxiety Disorder Assessment (GAD-7) [Anxiety], Assessment of Quality of Life (AQoL), Work Productivity and Activity Impairment (WPAI)
Timepoint:	at 6, 12, 18 and 24 months post baseline; also 6 and 12 months post intervention

Outcome measures and collection time points							
Measure	Base line	6 mth	12 mth	18 mth	24 mth	6 mth POST	12mth POST
Demographic and clinical measures:							
Demographic data, duration of diabetes	X						

 Demographic data, duration of diabetes at baseline only – to ensure similar characteristics of both the intervention and control groups. 							
Biometric measures; weight, BMI, girth, BP	X	X	X	X	X	X	X

 To review changes in metabolic parameters Time points to allow for intensification of treatment as deemed required Based on evidenced based guidelines/ peer-reviewed literature for timely treatment 							
Co-morbidities, medications	X		X		X		X

 To review changes (improvement/deterioration) in other co-morbidities as a result of treatment for obesity Review interval increased as changes in medication and disease profiles require review time, further based on timelines for review and assessment in peer-reviewed literature. 							
Edmonton obesity staging	X		X		X		X

 The Edmonton obesity staging system independently predicted increased mortality even after adjustment for contemporary methods of classifying adiposity (Padwal et al., 2011). The Edmonton obesity staging system may offer improved clinical utility in assessing obesity-related risk and prioritizing treatment. The project is targeting gradual weight loss that is linked to sustained weight loss – thus timing for assessment are linked to overall weight loss and potential co-morbidity reduction as estimated in peer reviewed literature 							
Sleepiness Scale	X		X		X		X

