
 1. Patient attends Diabetes Clinic 2. Pre-assessment includes physical measurements (BMI, BP) and HbA1c by CDE. Plus; Psychological Distress PHQ-9 and GAD-7, QoL SF-36v2, Assessment of Quality of Life (AQoL) and Work Productivity and Activity Impairment (WPAI). The above data will be collected by a research assistant and not the clinicians to prevent impact of 'treatment as usual'. 3. Patient reviewed by endocrinologist and management is diabetes and endocrine focused 4. Screening may include HbA1c, lipids, vitamin B12 and folates, TFTs, LFTs, ACR, eGFR 5. Referral to diabetes educator as needed for ongoing education if HbA1c above target 6. Referral to psychologist as required if patient raises psychosocial problems during consultations with either CDE or endocrinologist 7. Referral to dietitian if HbA1c > 9% in type 2 diabetes 8. Adhoc referral for bariatric assessment if BMI >40 and failed attempts at weight loss 	
 1. Patient attends AMOS Clinic 2. (a) Pre-assessment includes physical measurements (BMI, BP, girth) and HbA1c by CDE. (b) Universal screening - completion of scales to support planned assessment and care: 
 • Psychometric (Psychological Distress PHQ-9 and GAD-7, QoL SF-36v2 and AQoL, WPAI) • Epworth Sleepiness Scale • Absolute cardiovascular risk • Edmonton Obesity Staging (c) Review with physiotherapist for: 
 • Assessment for physical functioning performed • Completion of McCaffery Pain Assessment scale 3. (a) According to psychometric scales patient is triaged into psychologist for 1:1 or group session (b) Patient booked into physiotherapist for 1:1 or group sessions (c) According to dietitian assessment patient seen 1:1 or booked into group program (program facilitated by psychologist and dietitian with focus on identification of barriers) 4. Patient reviewed by endocrinologist and management is diabetes/endocrine and obesity focused 5. Screening for metabolic pathology request provided as per control group with addition of leptin and ketones (to identify weight loss and ketosis) and vitamin D In addition, assessment and review by dietitian to support development of treatment plan. 6. Treatment Plan agreed: 
 • Weight Loss goals determined • Referral as relevant to: 
 ○ Other health professional/specialist (sleep apnoea or pain management assessment if applicable) ○ Community Based Weight /Pain management programs (Stanford - GTMOL, OPAL) • Resistant or balance training • Medicines alteration and/or titration • Behaviours Modification and Self-Maintenance awareness 7. Initiation of Orlistat if BMI > 35 and < 2% weight loss after 3 months 8. Referral for bariatric assessment if deemed suitable and after 12 months failed treatment.

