Again although weight management is an important issue in the care of people with type 2 diabetes it is not the focus of the clinic; basic advice is provided in diet and physical activity by diabetes educators. Limited state funded dietetic services are utilised in the care of paediatrics with diabetes and generally adult individuals with type 1 and some with type 2 with pre-existing co-morbidities. Individuals with weight issues who are referred to state funded dietetic services for individualisation of advice are presented with a letter indicating that they ‘are not likely to be seen so will not be placed on a wait list’ and a list of private dietitians is provided. The same issue prevails as listed above in relation to financial capacity of the individuals. Thus, the majority of people with type 2 diabetes without co-morbidities or co-morbidities that are controlled, will not have personalised calculations of energy requirements needed and specific advice on the particular caloric decreased required to provide weight loss. In addition, the reasons behind eating behaviour and weight gain are more often from a psychology basis and/or related to funding of differing food types. Another limited health professional resource in the north west.

Methodology *(continue)*

Management of Cross Contamination TSRAC QUESTION 3 (Response)

- Randomisation will be achieved by method listed above
- Cross contamination is managed by several means:
 - The clinics are run on alternate days – thus patients are unlikely to come across each other – they may within the community as they would with any other RCT
 - The interventions which include multidisciplinary assessment and care, the use of orlistat and potentially bariatric surgery if identified as a suitable candidate requires assessment and referral – the control group patients will not have the assessments performed routinely and/or be in the setting to have these referrals created
 - The intervention group utilises a different credentialled diabetes educator than the ones used in the traditional (usual care) diabetes clinic
 - The endocrinologist involved in this study will mainly be involved in the AMOS clinic – during other clinics he will be seeing patients with type 1 diabetes of lower BMI who do not meet the criteria and due to different disease process their needs will differ
 - An alternate endocrinologist not involved in AMOS will see the control group within the traditional (usual care) diabetes clinic

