This study looks at the effects of care that is tailored to obesity. Patients invited to the study will be told about what they will need to do if they decide to be involved. They will be asked to provide written consent before being placed at random to the treatment group or normal care. Participants in the control group will receive routine care as part of the normal Adult Diabetes Clinic. Participants in the intervention group will complete a number of hand written assessments about sleep, pain, stress and/or how they have been feeling. Some measurements of body shape will be taken as well as some blood tests each 6 months. Some of these are routine tests for normal care and others are specific to the study. All participants will attend the service each 3 months – that is 4 times per year – these visits may last 30 to 90 minutes. At these times they may see other health professionals such as a physiotherapist, psychologist or dietitian – this will be on an individual basis at first and then may be in a group format. The group programs will involve learning about ways to stop the cycle of obesity and/or some physical activity. If no weight loss is achieved a dose of Orlistat will be suggested for a 3 month period. The participants will be contacted by the research assistant to arrange a time for their follow-up visits and to see how they are doing overall. If suitable and willing the participants may be referred to see a surgeon to discuss other options.

Nature of Existing Relationships between Potential Participants/Research team and Voluntary Consent

A majority of the participants will have had a past and/or current relationship with a number of the health professionals involved in the research study group. Potential participants will be clearly informed that their relationship with any of the investigations or staff involved in their medical care will not be influenced by their choice to participate or not to participate.

Potential participants will be assured that the decision to participate is voluntary and will have no influence on their relationship with medical or allied health professional staff, the research team or the THO-North West.

Impact of the research on the Relationship between Participants and the Researcher

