- Participants may directly benefit from participation in the study as a result of improvements in metabolic markers
- The early identification and management of secondary complications of obesity.
- A reduction in absolute cardiovascular risk.
- An improvement in glycated haemoglobin - or diabetes control.
- A potential reduction in body weight.

Risk of Harm

Low Risk – It is possible that participants may find some of the physical activities challenging and/or psychological sessions distressing. However, the study protocol directs those with higher levels of stress for therapies to reduce anxieties and distress. These are measured throughout the study at 6 month intervals.

Some participants will be referred for bariatric surgery. This surgery is associated with complications and adverse events. These are not a result of the study per se as the surgery is not experimental and is an established clinical treatment recommended in current national guidelines.

Other Risks

There are no foreseeable risks to the research team or the organisation.

Commercial Benefits of the Research for Investigators and Sponsors

There is no anticipated commercial benefit arising from the research for the investigators and/or sponsor

Risk of Harm as a Result of Dissemination

All data will be aggregated and de-identified and thus there is no foreseeable risk of harm when results are disseminated.

Mechanisms to monitor the Project

- The research will be conducted under the supervision of a steering committee comprised of members of the clinical team caring for the patients, experts in population health and with academic oversight.
- The clinic itself will operate under the supervision of the usual clinical governance of the North West Tasmanian Health Organisation (THO). All providers are staff members of THO North West, are credentialed to provide the clinical services outlined in the model and are subject to the safety and quality monitoring and reporting requirements of the North-West Regional Hospital, an accredited Australian public hospital.
- Regular monthly to 2 monthly meetings of the study investigators to monitor the conduct and progress of the study, and to manage change, problems and timelines.
- Meetings will review; participant recruitment rate, follow-up of participants according to key outcome timelines, reasons for attrition, data collection/entry and related issues, need for early termination of study.

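### Change in recorded co-morbidities is read as an effect of treatment, yet screening and referral for sleep, pain and function are systematic only in the AMOS arm, so the comparison mixes detection with treatment effect

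*Protocol*

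**What the plan says.** The table of outcome measures and collection time points (Protocol, Outcomes) has a row for co-morbidities and medications at baseline, 12 months, 24 months and 12 months post intervention. Its stated purpose is "To review changes (improvement/deterioration) in other co-morbidities as a result of treatment for obesity". The row carries no arm restriction and no rule for telling a newly found condition from a newly developed one.

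The table of differences between the two arms places three assessments in the AMOS column only: "Epworth Sleepiness Scale", "Assessment for physical functioning performed" and "Completion of McCaffery Pain Assessment scale". Referral for sleep apnoea or pain assessment is also listed only there. Management of Cross Contamination relies on this difference as a safeguard: "the control group patients will not have the assessments performed routinely and/or be in the setting to have these referrals created". The Lay Description of Participation agrees: "Participants in the intervention group will complete a number of hand written assessments about sleep, pain, stress and/or how they have been feeling". For controls, the data assigned to a research assistant are physical measurements, HbA1c and the mood, quality-of-life and work scales.

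Expected Benefits to Participants includes "The early identification and management of secondary complications of obesity". The note under the sleepiness scale sets its time points to leave room for referral, assessment and treatment of a diagnosed sleep disturbance.

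**The concern.** Finding co-morbidities is part of what AMOS does. When the chance that a condition is written down depends on the arm, a count of recorded conditions over time does not measure the same thing in the two arms. A patient with undiagnosed sleep apnoea at entry may gain a diagnosis by month 12 in AMOS and none in usual care, although both were equally ill throughout.

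A reader of the 12- and 24-month co-morbidity data could then conclude that AMOS worsens co-morbidity when it only finds more of it, or could miss a true improvement. This touches the objective on morbidity risk. It may also touch Edmonton staging, a named secondary outcome, if these diagnoses feed into the stage.

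**Working it through.** **Does the plan create unequal detection?**

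| Element | AMOS | Usual care |
|---|---|---|
| Sleepiness scale | Universal screening | Not listed |
| Pain scale, functional assessment | Physiotherapist review | Not listed |
| Sleep apnoea or pain referral | Part of the treatment plan | Setting does not generate it routinely |
| Presented pain | As above | Passed to the GP; private physiotherapy offered but seldom taken up |

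The last row comes from the section on usual care in the rural setting. Control detection is therefore lower, not nil.

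**When is the condition recorded?** Under Study Intervention the physiotherapist assesses pain and capacity for activity at entry, so those findings can be recorded as baseline conditions. The lag wording in the outcome table concerns sleep disturbance only. Post-baseline recording of a pre-existing condition is thus best supported for sleep disturbance.

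**Does anything correct for it?** The protocol promises post-hoc accounting in two places. One is for an occasional extra assessment in a control patient (Rationale for Study Design). The other is for care received through other pathways (Orlistat as the Pharmaceutical Intervention and Bariatric Surgery). Neither addresses systematic detection in one arm.

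**The plan's sample size.** No stated figure bears on detection; the only one used below is 106 per arm. It reproduces: with d = 0.5, two-sided alpha 0.05 and power 0.95, n = 2(1.960 + 1.645)²/0.5² = 104 per arm, or 105 with the t distribution, against 106 stated.

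**Illustration.** The protocol gives no prevalence or detection rates, so u and s are assumptions. Let u be the share of each arm with an unrecorded condition at baseline, and s the share of these found by follow-up. With no treatment effect:

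- new recordings: p_A = u × s_A and p_C = u × s_C
- spurious gap = u × (s_A − s_C)
- chance of significance from a two-sided 0.05 test of two proportions, pooled standard error SE0 under the null, SE1 under the alternative, both tails counted.

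Worked case, u = 0.20, s_A = 0.50, s_C = 0.10: p_A = 0.10, p_C = 0.02, gap 0.08. SE0 = √(2 × 0.06 × 0.94/106) = 0.0326. SE1 = √((0.10 × 0.90 + 0.02 × 0.98)/106) = 0.0322. (0.08 − 1.96 × 0.0326)/0.0322 = 0.50, which gives 0.69.

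With s_A = 0.50 throughout:

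| u | s_C = 0.40 | s_C = 0.25 | s_C = 0.10 |
|---|---|---|---|
| 0.10 | 1 point; 0.06 | 2.5 points; 0.16 | 4 points; 0.40 |
| 0.20 | 2 points; 0.08 | 5 points; 0.28 | 8 points; 0.69 |
| 0.30 | 3 points; 0.10 | 7.5 points; 0.41 | 12 points; 0.87 |

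With equal detection the gap is 0 and the chance returns to 0.05. The result depends heavily on control detection, about which the protocol gives no figure.

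**The case against.** The strongest reply is that the protocol never specifies this comparison. Co-morbidity change is a row in a collection table, not a named primary or secondary outcome. The Analysis section describes no test of it, and the classification of new conditions may be set out in a statistical analysis plan that is not shown. This stands in part: a reader might infer that the plan counts new diagnoses as deterioration, but no scoring rule says so. What remains is that the protocol itself names deterioration as something to be read from these data and attributes it to treatment.

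A reader might also infer that detection happens in one arm only. The documents do not support that. Usual care recognises presented pain and passes it on; what fails is follow-through, which is not evidence that the condition goes unrecorded.

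Third, pain and function are assessed at entry, so they need not surface later as new. That stands, and it narrows the main mechanism to sleep disturbance.

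Finally, the bias runs against AMOS and cannot by itself produce a false claim of benefit. That is correct and limits the severity.

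**Conclusion.** The concern holds in a limited form. Recorded co-morbidity change is attributed to treatment while the means of finding co-morbidities differ by arm, and nothing in the protocol separates the two. The direction is clear: AMOS would look worse. The size is not known. At 20% unrecorded prevalence and 50% detection in AMOS, the chance of a spurious significant difference ranges from about 0.08 to 0.69 as control detection falls from 40% to 10%, and every one of those rates is assumed. Fisher's exact test, which the protocol also allows, would give somewhat lower figures at such small counts.

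A reader might go further and conclude that the Edmonton secondary outcome is masked. The protocol does not list the inputs to the stage and links only the timing of its assessment to a possible reduction in co-morbidity, so this can be raised only as a possibility. The two primary outcomes, HbA1c and body weight, and the sample size are untouched. The point deserves correction but does not threaten the trial's main conclusion.

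**What to change.** - State that conditions first recorded through AMOS-only screening or referral are reported separately as detection yield, a process outcome, and are not counted as deterioration.
- Base the between-arm comparison of co-morbidity change on conditions recorded at baseline, counting those found at the entry assessment as baseline, and on measures confirmed to be collected in both arms. This needs checking: the protocol says only that control screening may include lipids, LFTs and eGFR.
- Give the all-diagnoses comparison as a sensitivity analysis.
- Keep the Edmonton stage as the named secondary outcome, and add a sensitivity analysis that excludes conditions found only through AMOS screening.
- Reconcile the outcome-measures table, which shows the sleepiness scale, the pain scale and Edmonton staging without arm restriction, with the table of arm differences (which lists all three for AMOS only), Management of Cross Contamination and the Lay Description.

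The cost is mainly wording and analysis work, with no change to the sample size. Each condition needs a note of how and when it was first recorded. The downside is that the main co-morbidity comparison leaves out some genuinely new conditions; the all-diagnoses sensitivity analysis would show them.
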